Recent anatomic studies by Short et al. confirmed the innervation of the anterior capsule of hip joint to be the obturator nerve, accessory obturator nerve, and femoral nerve. These studies also evaluated the relationship with these nerves and other bony or soft tissue landmarks visible by ultrasound guidance [15]. Previous studies have found histologically that the anterior capsule has predominantly nociceptive fibers, while the posterior capsule is largely made up of mechanoreceptors [16]. The pericapsular nerve group (PENG) block was introduced to target and block these articular branches providing innervation to the hip. This regional anesthetic technique was described in 2018 by Giron-Arango et al. for acute analgesia related to hip fractures [17]. Given the case reports showing the efficacy of PENG blocks for hip fracture surgeries, we sought to investigate the analgesic efficacy of PENG blocks for primary and revision THAs. The PENG block targets only the sensory branches and not the posterior mechanoreceptors; there is a potential motor-sparing effect which is desirable for early ambulation, better physical therapy, and earlier discharge. The effective analgesia and early ambulation provided by such regional anesthesia block may have positive impact on patient's mood, sleep, appetite and overall feeling of well-being. A similar postoperative recovery study

protocol has been proposed for anterior quadratus lumborum blocks for THA (18). It remains unclear whether PENG block provides sufficient analgesia and improves the quality of post-operative recovery after primary THA.

The ideal regional anesthesia technique for THA will provide adequate postoperative analgesia, reduced opioid requirements, early ambulation and physical independence. The aim of this single center, double blind RCT is to confirm the efficacy of PENG block for postoperative recovery with respect to parameters mentioned above.

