3.0 OBJECTIVE(S) & HYPOTHESIS

The objectives of the study are as follows:

1. Determine the efficacy of PENG for primary THA compared to no peripheral nerve block on Quality of Recovery (QoR) after surgery.
2. Determine the efficacy of PENG for analgesia, post-operative mobilization, side effects, patient satisfaction and length of hospital stay for THA compared to no peripheral nerve block

We hypothesize that patients receiving PENG prior to primary THA will have superior quality of recovery, compared to the patients who do not receive PENG block.

Trial design: This randomized-controlled, double-blind, single-center, pragmatic, superiority trial with the two-parallel group (1:1 allocation) is designed to assess the efficacy of PENG block compared to no-block in improving the QOR for patients undergoing primary THR. The unit of randomization will be individuals (not clusters). The QOR-15 questionnaire was chosen as a measure of efficacy because it is an extensively validated measure of patient-assessed quality of recovery after surgery, having been demonstrated over a variety of clinical settings. Allocation ratio of 1:1 would allow the research question with a minimal number of subjects.

METHODS

Study setting: The study will be conducted at UAB Highlands Hospital.

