9.0 STATISTICAL CONSIDERATIONS

General Data Analysis Plan:

The distribution of the continuous factors will be examined using data visualization techniques such as q-q plots and the Shapiro-Wilk test. All normally distributed demographic and continuous variables will be expressed as means and standard deviations; categorical factors will be expressed as proportions. For non-normal data, the medians and inter quartile ranges will be displayed. For data that are normally distributed, Student's t-test will be used to compare the groups. For data that are not normally distributed, a Mann-Whitney tests will be used for comparisons. Chi-square or Fisher's exact tests will be used to analyze categorical data. Time to event data such as distance of first ambulation will be analyzed using Kaplan-Meier curves. The planned sub-group analysis will be conducted for GA vs. Spinal using a 2x2 ANOVA test. For all comparisons, a value of $p < 0.05$ will be considered statistically significant. Statistical analyses will be performed using SAS for Windows, version 9.2.

Statistical Power and Sample Size Estimates: Fifty-six patients in each group are required to detect a Minimal Clinically Important Difference (MCID) of 8 points for QoR-15 score assuming a standard deviation of 15 points using data from previous studies (19, 20) for 5% significance level and 80% power.

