Data were summarised using means and standard errors (SE) for continuous outcomes or counts and percentages for categorical outcomes. Two-sample t-tests and chi-square tests were used to compare the two groups. Normality for continuous outcomes was assessed using probability plots and the Shapiro-Wilk test for normality. For any outcomes where normality could not be reasonably assumed, medians and interquartile ranges were reported instead of medians and standard errors, respectively, and the Wilcoxon rank sum test was used in place of the t-test. A 95% confidence interval for differences in means (for continuous outcomes) or relative risks (for categorical outcomes) were calculated. For any non-normally distributed continuous outcomes, asymptotic Hodges-Lehmann confidence limits were calculated.¹⁶ A p-value < 0.05 was considered statistically significant. SAS version 9.4 (SAS Institute Inc., Cary, NC) was used to conduct all statistical analyses.

Sample size calculation

A difference of 8 points is widely accepted as a minimal clinically important difference (MCID) for QoR-15 scores for perioperative interventions.¹⁷ A previous study showed a median QoR-15 score of 115 in the control group for the THA population.¹⁸ Assuming an increase to 123 in the QoR-15 score would be clinically relevant and a standard deviation of 15 points, we estimated that fifty-six patients were needed in each group for 80% power at a 5% significance level.

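### Efficacy on secondary outcomes is framed as confirmatory while every comparison is called significant at p < 0.05, with no testing order, gate or exploratory label

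*Combined protocol and SAP*

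**What the plan says.** **What is confirmatory.** Section 6.0 (Measured Outcomes) names one primary outcome, QoR-15 at 24 hours. The hypothesis in section 3.0 concerns quality of recovery only. The sample size in section 9.0 rests on QoR-15 alone: a "Minimal Clinically Important Difference (MCID) of 8 points for QoR-15 score", "assuming a standard deviation of 15 points", "for 5% significance level and 80% power".

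**Where the claims go further.** The closing sentence of section 2.0 aims to "confirm the efficacy of PENG block for postoperative recovery with respect to parameters mentioned above". The sentence before it lists those parameters: postoperative analgesia, opioid requirements, ambulation and physical independence. Objective 2 in section 3.0 reads "Determine the efficacy of PENG for analgesia, post-operative mobilization, side effects, patient satisfaction and length of hospital stay".

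**The decision rule.** Section 9.0 states "For all comparisons, a value of $p < 0.05$ will be considered statistically significant". It comes directly after "The planned sub-group analysis will be conducted for GA vs. Spinal using a 2x2 ANOVA test". The Summary (1.0) repeats the threshold, as does the statistical text after the QoR-15 form in the Appendix: "A p-value < 0.05 was considered statistically significant". No section orders the secondary outcomes, adjusts for their number, makes them conditional on the primary, or calls them or the subgroup analysis exploratory. The only ranking is primary versus secondary.

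**The concern.** Unadjusted secondary outcomes are common and do little harm when they are described as supportive. Here the stated aim gives several of them confirmatory standing, and the decision rule gives each one a full 5%. If QoR-15 at 24 hours shows no difference, nothing in the plan prevents one p < 0.05 on, say, opioid use or ambulation from being reported as confirmed efficacy. The error rate of that claim is the chance that at least one of many comparisons crosses the threshold, which is well above the rate for any single one.

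**Working it through.** **1. The plan's own figure.** Inputs from section 9.0: difference 8, SD 15, 5% level, 80% power. Sidedness is not stated.

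n per arm = 2 × (1.960 + 0.842)² × 15² / 8² = 55.2, rounded up to 56.

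This reproduces the stated 56 per arm. A one-sided test would need 44, so two-sided 5% is taken as the intended level.

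**2. Counting the secondary comparisons** (section 6.0, Measured Outcomes).

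| Outcome | Comparisons |
|---|---|
| QoR-15 at 48 h | 1 |
| Opioids: intraoperative, 24 h oxycodone, 24 h hydromorphone | 3 |
| Nausea, vomiting, itching | 3 |
| Independence in mobility and transfers | 1 |
| Ambulation distance | 1 |
| Satisfaction | 1 |
| Hours to discharge | 1 |
| **Non-pain subtotal** | **11** |
| VAS: 4 times × rest and movement | 8 |
| Highest pain score in 24 h | 1 |
| **Total** | **20** |

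**3. Error rate if PENG affects no outcome.** With k independent tests:

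- P(at least one p < 0.05) = 1 − 0.95^k. For k = 11: 1 − 0.95¹¹ = 43%. For k = 20: 1 − 0.95²⁰ = 64%.
- P(at least one favouring PENG) = 1 − 0.975^k. For k = 11: 24%. For k = 20: 40%.

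The outcomes are probably correlated, and the documents give no correlations. I therefore assumed a common correlation ρ between the test statistics. With c = 1.96, φ the normal density and Φ its distribution function:

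P(any) = 1 − ∫ φ(f) [Φ((c − f√ρ)/√(1−ρ)) − Φ((−c − f√ρ)/√(1−ρ))]^k df.

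For results favouring PENG, drop the second Φ term.

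| k | Event | ρ = 0 | 0.3 | 0.5 | 0.7 |
|---|---|---|---|---|---|
| 5 (one per objective-2 domain) | any | 23% | 21% | 18% | 15% |
| 10 (11 without ambulation distance) | any | 40% | 35% | 29% | 21% |
| 11 (non-pain) | any | 43% | 37% | 30% | 22% |
| 11 | favours PENG | 24% | 19% | 15% | 11% |
| 20 (all) | any | 64% | 54% | 42% | 29% |
| 20 | favours PENG | 40% | 28% | 21% | 14% |

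The reference values for a single test are 5% (any) and 2.5% (favours PENG).

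**4. Ambulation distance.** Section 9.0 names only Kaplan-Meier curves for this outcome and no between-group test. It is counted because the p < 0.05 rule covers all comparisons. The k = 10 row shows that dropping it changes little.

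**The case against.** **The primary is protected.** There is one primary outcome, one hypothesis and a sample size built on it, and the Summary states the aim as postoperative recovery without listing other parameters. The broader aim is one sentence in the Background section, supported by objective 2. This stands: the secondary outcomes do not inflate the error of the primary test. It does not remove the mismatch, because the broader aim and the all-comparisons rule are both in the plan and nothing limits either.

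**The 5% is per comparison.** The plan never promises a family-wise rate, and a claim about one secondary outcome named in advance keeps its 5%. That is correct. The inflation concerns the at-least-one event, which matters because the plan singles out no secondary outcome in advance.

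**The figures are unconditional.** The worrying case is a null primary. Conditioning on a non-significant primary that is equally correlated with the secondaries lowers the 11-test chance of a result favouring PENG only slightly: to about 14% (from 15%) at ρ = 0.5 and 10% (from 11%) at ρ = 0.7.

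**Intervals are already planned.** The statistical text in the Appendix provides 95% confidence intervals for mean differences and relative risks, and Hodges-Lehmann limits for non-normal outcomes. This is part of the remedy and deserves credit. The same text keeps the p < 0.05 rule, however, and does not mention the ANOVA.

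**The ANOVA.** A reader might infer that the 2x2 ANOVA gives a second chance at the primary question through its block main effect. The documents do not support saying so outright. Section 9.0 calls it a subgroup analysis, names no outcome for it and does not say which term will be reported. A second test of the primary would arise only if the ANOVA were run on QoR-15, with an unweighted main effect and unequal GA and spinal shares. Under those assumptions, the chance that either the two-sample test or the main effect is falsely significant is 6.0% at 60% spinal and 8.6% at 90%. A main effect weighted by the shares would add nothing.

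**Conclusion.** The point holds as a gap between what the plan says it will confirm and what its error control supports. If PENG affects nothing, at least one of the 11 non-pain secondary comparisons is falsely significant with a chance of about 22% to 43%, and at least one falsely favours PENG with a chance of about 11% to 24%. With all 20 comparisons the ranges are about 29% to 64% and 14% to 40%.

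These figures rest on no effect on any outcome, on assumed common correlations from 0.7 to 0, and on counting each listed measure as one test. If PENG truly works on some outcomes, fewer false positives are possible.

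A reader might infer that a spurious secondary success is likely. The numbers do not show that: the chance of one favouring PENG stays at or below 40% even with 20 independent tests. Several times the single-test rate is the accurate description. Nor is the validity of the 24-hour QoR-15 test in question.

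**What to change.** 1. In section 9.0, and in the statistical text in the Appendix, replace the general p < 0.05 sentence with wording to this effect: *QoR-15 at 24 hours, tested at two-sided 5%, is the only confirmatory test. All secondary outcomes and the GA/spinal analysis are exploratory and are reported with 95% confidence intervals; a nominal p < 0.05 on any of them is not evidence of confirmed efficacy.* Align the Summary. The Appendix text is in the past tense, so if the analysis is already done, the same statement can govern the report.
2. In section 2.0, limit the confirmatory aim to QoR-15 at 24 hours. In objective 2, speak of estimating the effect instead of determining efficacy.
3. If the 2x2 ANOVA is run on QoR-15, report the block-by-anaesthetic interaction with its interval as the subgroup result, and do not treat the block main effect as a second primary test.
4. Optional, if a formal secondary claim is wanted: list a few secondary outcomes in fixed order, each tested at two-sided 5%, only after the primary is significant and stopping at the first non-significant result. This is cheaper than a Bonferroni split: for a standardised effect of 8/15 with 56 per arm, power falls from 81% at 0.05 to 42% at 0.05/20 = 0.0025.

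**Cost.** Items 1 to 3 are wording changes. The primary keeps its 5% and 56 per arm, and no extra data or patients are needed. The downside is that a lone significant secondary outcome can no longer be presented as proof of efficacy.

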10.0 PATIENT SAFETY AND DATA SECURITY MONITORING

- Does this research involve children (i.e. <18 years of age)? no
- Assessment of Level of Risk: High Medium Low Not applicable

[Click here to enter text.](#)

- Reporting adverse events:

A data and safety monitoring plan will be implemented by Drs. [name] and [name] to ensure that there are no changes in the risk/benefit ratio during the course of the study and that confidentiality of research data is maintained. This will be achieved by close following of study participants to screen for adverse events during data collection phase. Investigators and study

personnel will meet either electronically or in person, monthly (more often if needed) during active participant enrollment to discuss the study (e.g., study goals and modifications of those goals; subject recruitment and completion; progress in data coding and analysis; documentation, identification of adverse events or research subject complaints; violations of confidentiality) and address any issues or concerns at that time.

The mechanisms for HIPAA compliance [including a detailed electronic personal health information (PHI) data path]:

Mechanisms for HIPAA compliance: The de-identified study data will first be entered onto standardized, preprinted data collection sheets that will have no patient identifiers on them such as name, medical record number and date of surgery. The study data will be collected and stored on a secure research server maintained by the Department of Anesthesiology. The research server is HIPAA compliant, has researcher specific restricted access, and is password protected. This research server is backed up to another secure research server at a different location. The list of patients participating in the study with their medical record numbers and dates of surgery will be kept separately and securely in a locked filing cabinet in the locked office of [name] and will be destroyed, after final data analysis, using the UAB contracted confidential shredding service. The original paper data collection forms will be disposed of using the UAB contracted confidential shredding service after the de-identified data have been transferred to the password-protected, computer database. From that point in time onward, all study participants will be identified only by their individual study specific number, both on the above server and the backup server. All personnel who are involved in the design or conduct of this research study will have successfully completed

required IRB training which includes the importance of measures to protect patient confidentiality.

References:

Appendix:

QOR-15 FORM

QoR-15 Patient Survey

Date: ___/___/___ Study #: _____

Preoperative Postoperative

PART A

How have you been feeling in the last 24 hours?

(0 to 10, where: 0 = none of the time [poor] and 10 = all of the time [excellent])

1. Able to breathe easily None of the time 0 1 2 3 4 5 6 7 8 9 10 All of the time

2. Been able to enjoy food None of the time 0 1 2 3 4 5 6 7 8 9 10 All of the time

3. Feeling rested None of the time 0 1 2 3 4 5 6 7 8 9 10 All of the time

4. Have had a good sleep None of the time 0 1 2 3 4 5 6 7 8 9 10 All of the time

5. Able to look after personal toilet and hygiene unaided None of the time 0 1 2 3 4 5 6 7 8 9 10 All of the time

6. Able to communicate with family or friends None of the time 0 1 2 3 4 5 6 7 8 9 10 All of the time

7. Getting support from hospital doctors and nurses None of the time 0 1 2 3 4 5 6 7 8 9 10 All of the time

8. Able to return to work or usual home activities None of the time 0 1 2 3 4 5 6 7 8 9 10 All of the time

9. Feeling comfortable and in control None of the time 0 1 2 3 4 5 6 7 8 9 10 All of the time

10. Having a feeling of general well-being None of the time 0 1 2 3 4 5 6 7 8 9 10 All of the time

PART B

Have you had any of the following in the last 24 hours?

(10 to 0, where: 10 = none of the time [excellent] and 0 = all of the time [poor])

11. Moderate pain None of the time 10 9 8 7 6 5 4 3 2 1 0 All of the time

12. Severe pain None of the time 10 9 8 7 6 5 4 3 2 1 0 All of the time

13. Nausea or vomiting None of the time 10 9 8 7 6 5 4 3 2 1 0 All of the time

14. Feeling worried or anxious None of the time 10 9 8 7 6 5 4 3 2 1 0 All of the time

15. Feeling sad or depressed None of the time 10 9 8 7 6 5 4 3 2 1 0 All of the time

Fig. 2. The quality of recovery score (QoR)-15 questionnaire.

Statistical analysis

Data were summarised using means and standard errors (SE) for continuous outcomes or counts and percentages for categorical outcomes. Two-sample t-tests and chi-square tests were used to compare the two groups. Normality for continuous outcomes was assessed using probability plots and the Shapiro-Wilk test for normality. For any outcomes where normality could not be reasonably assumed, medians and interquartile ranges were reported instead of medians and standard errors, respectively, and the Wilcoxon rank sum test was used in place of the t-test. A 95% confidence interval for differences in means (for continuous outcomes) or relative risks (for categorical outcomes) were calculated. For any non-normally distributed continuous outcomes, asymptotic Hodges-Lehmann confidence limits were calculated.¹⁶ A p-value < 0.05 was considered statistically significant. SAS version 9.4 (SAS Institute Inc., Cary, NC) was used to conduct all statistical analyses.

Sample size calculation

A difference of 8 points is widely accepted as a minimal clinically important difference (MCID) for QoR-15 scores for perioperative interventions.¹⁷ A previous study showed a median QoR-15 score of 115 in the control group for the THA population.¹⁸ Assuming an increase to 123 in the QoR-15 score would be clinically relevant and a standard deviation of 15 points, we estimated that fifty-six patients were needed in each group for 80% power at a 5% significance level.
